#### **4.1.4 Pharmacokinetics Analysis Set**

The PK analysis set includes all patients who receive at least 1 dose of ADCT-402 with evaluable and sufficient concentration-time data to permit reliable estimation of ADCT-402 exposure, and with no major or critical protocol deviations related to ADCT-402 administration.

4. Patient who received the wrong treatment or incorrect dose. For example,
  - Actual dose of study drug was more than 15% greater than protocol defined planned dose level.
  - Patient started next cycle less than 18 days later after Day 1 of the most recent treatment cycle.

Important protocol deviations will be listed.

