6.2.1 Pharmacokinetic Assessments

The PK profile of ADCT-402 (total antibody; $DAR \geq 0$), PBD-conjugated antibody ($DAR \geq 1$), and free warhead SG3199 will be assessed by a central laboratory. Additional PK blood samples will be collected, at the discretion of the Investigator, during any visit where toxicity is observed. A PK and ADA sample will also be collected concurrently with any other blood draw to assess safety (e.g., Unscheduled Visit), if possible. All PK samples will be evaluable as long as actual collection times are recorded.

To understand the metabolic disposition of ADCT-402 in humans, samples remaining after PK analysis is complete may be pooled among patients for potential metabolite identification.

The PK profile will include determination of: maximum concentration (C_{max}), time to C_{max} (T_{max}), area under the concentration-time curve from time zero to the last quantifiable concentration (AUC_{0-last}), area under the concentration-time curve (AUC) from time zero to the end of the dosing interval ($AUC_{0-\tau}$), area under the concentration-time curve from time zero to infinity ($AUC_{0-\infty}$), accumulation index (AI), volume of distribution at steady-state (V_{ss}), mean residence time (MRT), terminal elimination phase rate constant (λ_z), terminal half-life ($T_{1/2}$), clearance (CL), and volume of distribution (V_z).

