7.4 Analysis Sets

Five analysis sets will be used in this study:

- The Safety analysis set will consist of all patients who receive study drug
- The DLT-evaluable analysis set will consist of all patients in Part 1 who receive study drug and excludes patients who discontinue study drug during Cycle 1 without experiencing a DLT.
- The Efficacy analysis set will consist of all patients with valid baseline data who receive who receive at least 2 doses of study drug or who have documented progression of disease at any time after the first dose of study drug.
- The PK analysis set will consist of all patients who receive study drug and have sufficient concentration data for PK analysis.
- The Pharmacodynamic analysis set will consist of all patients who receive study drug and have sufficient concentration data for analysis.

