7.6.3 Pharmacokinetic and Pharmacodynamic Analyses

Pharmacokinetic endpoints for RB4v1.2, PBD-conjugated RB4v1.2, and free warhead SG31999 will be evaluated for all patients using noncompartmental analysis. Data for PK parameters will be summarized in tables and individual data will be listed.

[REDACTED]

[REDACTED]

[REDACTED]

[REDACTED]

[REDACTED]

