#### 3.3 Modifications to the statistical section of the protocol

The efficacy analysis set was defined in the protocol as all patients with valid baseline data who receive at least 2 doses of study drug or who have documented progression of disease at any time after the first dose of study drug. However, a few patients received 200 µg/kg on an every 6 weeks (Q6W) schedule and their disease assessments were performed before the second dose. These patients should be considered as evaluable for efficacy analysis.

Therefore, the efficacy analysis set is updated in the SAP to include all patients who have received at least one dose of ADCT-402 with a valid baseline and at least one valid post-baseline disease assessment or patients who have documented progression of disease or death at any time after the first dose of study drug.

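### SAP 4.1.4 drops a whole patient from the PK set for a major or critical dosing deviation in any cycle, a rule that protocol 7.4 does not contain and SAP 3.3 does not declare

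*SAP*

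**What the plan says.** The protocol defines the PK set in 7.4: "The PK analysis set will consist of all patients who receive study drug and have sufficient concentration data for PK analysis". Two other protocol sections point the same way. Section 6.2.1 states: "All PK samples will be evaluable as long as actual collection times are recorded". Section 7.6.3 says that the PK endpoints "will be evaluated for all patients using noncompartmental analysis".

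The SAP defines it in 4.1.4. The unit of inclusion is the patient: "The PK analysis set includes all patients who receive at least 1 dose of ADCT-402 with evaluable and sufficient concentration-time data". It then adds a condition, "and with no major or critical protocol deviations related to ADCT-402 administration". No cycle, date or profile is attached to that condition.

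SAP 3.3 is the place for changes to the protocol's statistical section. It declares and explains one change: "the efficacy analysis set is updated in the SAP to include all patients who have received at least one dose of ADCT-402". It does not mention the PK set.

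The public copy of the SAP also shows the end of a list of important protocol deviations. Its item on wrong treatment or incorrect dose gives two examples: "Actual dose of study drug was more than 15% greater than protocol defined planned dose level" and "Patient started next cycle less than 18 days later after Day 1 of the most recent treatment cycle". By the table of contents this list belongs to SAP 4.3, not to 4.1.4.

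**The concern.** The SAP narrows a protocol-defined analysis set without saying so, and does it at the level of the patient. A dosing error belongs to one infusion and can distort the PK of that cycle and perhaps of later ones. It cannot alter concentrations measured before it. A patient-level rule with no cycle limit removes those earlier measurements as well.

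At stake is the final reporting of a secondary objective, the PK profile of total antibody, conjugated antibody and free warhead. Part 1 dose levels can be as small as three patients, so the loss of one matters most there. An undeclared change also means that a reader of the study report cannot tell, from the protocol and SAP 3.3, why treated patients with usable data are absent from the PK tables.

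**Working it through.** The plan states no figure that depends on the PK set, so there is nothing to reproduce. The check has three steps.

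**1. Compare the definitions.**
- Protocol 7.4: treated, with enough concentration data. No deviation criterion.
- SAP 4.1.4: treated, with enough data, and free of major or critical dosing deviations. No cycle limit.
- SAP 3.3: only the efficacy set is listed as changed.

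The SAP set can therefore only be equal to or smaller than the protocol set on this criterion, and the difference is undeclared.

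**2. Find when the informative PK data are collected.**
- Protocol 4.1.2: in Cycles 1 and 2, Day 1 samples are taken pre-infusion, at end of infusion, and 1, 3 and 6 hours later. From Cycle 3, Day 1 sampling is pre-infusion and end of infusion only.
- Protocol 4.1.3 to 4.1.5 and 4.1.7: samples on Days 2, 3, 5 and 15 are limited to Cycles 1 and 2.
- Protocol 4.1.6: Day 8 samples in Cycles 1 to 4.

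A first qualifying deviation after Cycle 2 thus comes after the intensive sampling. One boundary case needs care: an early start of Cycle 3 shortens the interval after the Cycle 2 dose, although it leaves Cycle 1 and the Cycle 2 samples already drawn untouched. An early start of Cycle 2 is different. It cuts the Cycle 1 interval short and changes the Cycle 2 pre-dose level, so it does touch the intensive profiles.

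**3. Size of the loss.**

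Inputs: 3 patients per level, or 6 after one DLT (protocol 3.2), and a conditional Part 1 cap of 10 (protocol 3.2). Share lost by one exclusion = 1/n:
- n = 3: 33%
- n = 6: 17%
- n = 10: 10%

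For scale only, take a 95% t-interval for a mean PK parameter, with half-width in SD units = t(0.975, n−1)/√n:
- n = 3 to 2: 2.48 to 8.98, ratio 3.6
- n = 6 to 5: 1.05 to 1.24, ratio 1.18
- n = 10 to 9: 0.715 to 0.769, ratio 1.07

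The visible text plans no such interval for PK. The 3.6-fold figure is a worst case at the smallest cohort, where the interval falls from 2 degrees of freedom to 1.

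The documents give no deviation rate, so the next figures rest on assumed rates. If a proportion q of patients has a qualifying deviation, the chance that a dose level loses at least one is 1 − (1 − q)^n. For q = 2%, 5% and 10%:
- n = 3: 6%, 14%, 27%
- n = 6: 11%, 26%, 47%
- n = 10: 18%, 40%, 65%

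Only some of these would lose profiles that preceded the deviation. With an assumed, independent risk c per cycle over an assumed 6 cycles, the chance that the first deviation falls after Cycle 2 is (1 − c)² × [1 − (1 − c)⁴]. For c = 1%, 2% and 5% this gives 3.9%, 7.5% and 16.7% of patients.

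**The case against.** The strongest reply is that the public text does not show enough to judge the rule. No visible passage defines major or critical. The visible list concerns important deviations, its first items are missing, and it belongs to another section. The text of SAP 4.10.1 on the PK method is not visible either and may already handle exclusions by profile and use the actual dose. This stands as a limit: the triggers are unknown and the remedy may be partly in place. It does not remove the wording of 4.1.4, which decides membership of the set by patient.

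A second reply is that protocol section 7 leaves technical detail to the SAP, and that the sentence in protocol 6.2.1 is about sampling times, not dosing errors. The reading of 6.2.1 is fair, so that sentence is support and not a contradiction. But a new ground for leaving patients out is more than elaboration, and the SAP itself treated a change to the efficacy set as one to declare.

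A third reply is that the practical loss is small. Small dose levels may be pooled (SAP 4), individual PK data will still be listed (protocol 7.6.3), and about 90 Part 1 patients over nine planned levels average 10 per level if all are used. For a Cycle 1 error, a profile-level rule would lose nearly as much. All of this stands and keeps the point minor.

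Two stronger readings are tempting. A reader might infer that the rule selectively removes the most highly exposed patients, because both visible examples raise exposure. The documents do not support this: the item covers any incorrect dose, which includes underdosing, and the list is incomplete. A reader might also infer that dose selection is affected. The protocol lets PK inform the steering committee's decisions, but nothing says that the committee uses the SAP's PK set.

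**Conclusion.** The point holds as an undeclared difference between protocol 7.4 and SAP 4.1.4 that, on the literal wording, can drop PK profiles collected before the deviation occurred. Each such case costs one patient's PK data at a dose level, between a third of a three-patient level and a tenth of a ten-patient level. How often this would happen is not known, and the direction of any bias cannot be assessed because the triggers are not visible.

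The conclusion assumes that 4.1.4 is applied as worded and that the unseen PK methods text does not limit it by cycle. The SAP tests no hypotheses, so no error rate or sample size is touched. It is a desirable correction, not a critical one.

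**What to change.** - Restore the PK set of protocol 7.4 in SAP 4.1.4.
- Apply the deviation criterion by profile. Drop from planned-dose summaries only the cycle affected by the deviation and any later cycle that it influences.
- Derive clearance and dose-normalised parameters from the actual dose. SAP 4.7.1 already calculates the dose given at each infusion, so the input exists.
- Flag the affected profiles in the listings.
- State which dosing deviations count as major or critical for this purpose, or point to the section that does.
- Declare and justify in SAP 3.3 any departure from protocol 7.4 that remains.

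The cost is a change of SAP wording and a profile-level flag in place of a patient-level one, which means slightly more programming. No new data are needed.

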#### **4.4 Demographic and Baseline Characteristics**

Demographic and baseline characteristics will be tabulated for the safety analysis set by dose level. Variables include the following:

- Sex (female, male)
- Race (white, black or African American, Asian, American Indian or Alaska native, native Hawaiian or other Pacific Islander, other)
- Ethnicity (Hispanic or Latino, not Hispanic or Latino)
- Age (years)
- Age group (< 65, ≥ 65 - < 75, ≥ 75 years)
- Height (cm)
- Weight (kg)
- Body mass index (kg/m^2)
- Eastern Cooperative Oncology Group (ECOG) performance status

Demographic and baseline characteristics data will be listed.

#### **4.5 Cancer History and Medications History**

Cancer history will be presented for the safety analysis set by dose level. Cancer history will include the following variables:

- Duration since diagnosis
- non-Hodgkin lymphoma subtype (diffuse large B-cell lymphoma, follicular lymphoma, chronic lymphocytic leukemia, mantle cell lymphoma, marginal zone B-cell lymphoma, Burkitt's lymphoma, lymphoplasmacytic lymphoma [Waldenstrom macroglobulinemia], other)
- Stage of disease (Stage I, II, III, IV; constitutional symptoms A, B; Subtype E, X, S)
- Cytogenetic analysis (results available yes, t(11;14), t(11q), +12, del(11q), del(13q), del(17p), t(14;18), t(8; 14), t(8;22), other)
- Immunophenotypic analysis (results available yes; IgVH status mutated, unmutated, not applicable; CD5, CD10, CD19, CD20, CD21, CD23, CD43, CD79b, BCL1, BCL2, BCL6, CYCLIN D1, ZAP70 negative, positive, not done)

Prior anticancer procedure or therapy will include the following variables:

- Number of lines of therapy/ regimens per patient
- Any prior radiotherapy for the current malignancy (yes, no)
- Any prior systemic therapy for the current malignancy (yes, no)
- Reason for stopping therapy (progression, toxicity, other)

- Best response (complete response [CR], partial response [PR], stable disease [SD], progressive disease [PD], not evaluable [NE])
- Any prior stem cell transplant (yes, no)
- Type of transplant (allogenic, autologous, both, other)
- Conditioning therapy (yes, no)

Medical and cancer history data will be listed. [REDACTED]

Prior anticancer radiotherapy, systemic therapy, and stem cell transplant data will be listed.

#### **4.6 Prior or Concomitant Medications (other than anticancer therapies)**

All medications taken within 14 days before dosing and until the end of the study are to be reported in the CRF pages.

All medications will be coded using the World Health Organization-Drug Dictionary (WHO-DD) and presented by dose level for the safety analysis set.

- Prior medications are those the patient used prior to first investigational product (IP) intake. Prior medications can be discontinued before first dosing or can be ongoing during the treatment phase.
- Concomitant medications are any treatments received by the patient concomitantly to any IP(s), from first dose (or start of the observation period) to the last dose + 30 days. A given medication can be classified both as a prior medication and as a concomitant medication. Concomitant medications do not include medications started 30 days after the last dose.

Any technical details related to computation, dates, and imputation for missing dates are described in Section 6.

Prior medications will be listed together with concomitant medications.

#### **4.7 Exposure to Treatment**

##### **4.7.1 Extent of ADCT-402 Exposure**

ADCT-402 exposure will be summarized for the safety analysis set by dose level. Duration of treatment, total number of cycles dosed, total dose received (in  $\mu\text{g}$  and  $\mu\text{g}/\text{kg}$ ), and average dose per cycle (in  $\mu\text{g}$  and  $\mu\text{g}/\text{kg}$ ) will be tabulated. When actual weight adjusted dose is needed, the last available weight before each infusion will be used. Dose administered at each infusion ( $\mu\text{g}$ ) is calculated by concentrated IP volume (in mL)\* 5 mg/mL \*1000 or serially diluted IP volume (in mL)/50\* 5 mg/mL \*1000; for partial infusion, multiply by (1-volume of dosing solution not administered [in mL]/ 50 mL).

Dose delays and dose reductions could also be analyzed if relevant. A cycle is delayed if it starts more than 3 days post- scheduled date.

Exposure data and infusion details will be listed together.

## 4.7.2 Prophylactic Medications for Hypersensitivity

Prophylactic medications for hypersensitivity will be listed only.

## 4.7.3 Subsequent Anticancer Therapy or Procedure

Patients' subsequent anticancer therapies or procedures including systemic therapy, radiation, transplant, or other, along with the start date of new anticancer therapy or procedure will be collected and listed only.

## 4.8 Safety Analyses

The summary of safety results will be presented by treatment group.

### General common rules

All safety analyses will be performed on the safety analysis set, unless otherwise specified, using the following common rules:

- The baseline value is defined as the last non-missing value or measurement taken up to the first dose in the study.
- The analyses of the safety variables will be essentially descriptive and no systematic testing is planned.
- If relevant, selected safety analyses will be summarized by age, sex, racial subgroups, and any pertinent subgroups.
- The toxicity grade according to the Common Terminology Criteria for Adverse Events (CTCAE) version 4.0 will be taken into account in the summary. For patients with multiple occurrences of the same event, the maximum grade is used. If a patient has both missing and non-missing severity grades for treatment-emergent adverse events (TEAEs) within the same preferred term (PT), the patient will be counted under the non-missing severity grade.

### 4.8.1 Dose-limiting Toxicities (Part 1)

DLT data will be listed for Part 1 of the study.

### 4.8.2 Adverse Events, Serious Adverse Events, and Deaths

#### 4.8.2.1 Analyses of adverse events

The primary focus of adverse event reporting will be on TEAEs. An adverse event (AE) will be considered to be a TEAE if it begins or worsens on or after first dose date and until 84 days (12 weeks) after the last dose date, or start of a new anticancer therapy/procedure, whichever comes earlier.

An AE occurring before the first dose or more than 84 days (12 weeks) after last dose date or after the start of a new anticancer therapy/procedure will not be included in TEAE displays, but will be listed as non-TEAEs.

If an AE date/time of onset (occurrence, worsening, or becoming serious) is incomplete, an imputation algorithm will be used to classify the AE as pre-treatment, TEAE, or post-treatment. The algorithm for imputing date/time of onset will be conservative and will classify an AE as a treatment-emergent unless there is definitive information to determine it is a non-TEAE (pre- or post-treatment).

Details on classification of AEs with missing or partial onset dates are provided in Section 6.

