6.3.2 Adverse Events

6.3.2.1 Definitions of Adverse Events

The Investigator is responsible for reporting all AEs that are observed or reported during the study, regardless of their relationship to study drug or their clinical significance.

An AE is defined as any untoward medical occurrence in a patient enrolled into this study regardless of its causal relationship to study drug. Patients will be instructed to contact the Investigator at any time after ICF signature if any symptoms develop.

A treatment-emergent AE (TEAE) is defined as any event not present before exposure to study drug or any event already present that worsens in either intensity or frequency after exposure to study drug.

A serious adverse event (SAE) is defined as any event that results in death, is immediately life threatening, requires inpatient hospitalization or prolongation of existing hospitalization, results in persistent or significant disability/incapacity, or is a congenital anomaly/birth defect. Hospitalization for elective procedures or for protocol compliance is not considered an SAE.

Important medical events that may not result in death, are life threatening, or require hospitalization may be considered SAEs when, based upon appropriate medical judgment, the event may jeopardize the patient or may require medical or surgical intervention to prevent any of the outcomes listed in this definition. Examples of such medical events include allergic bronchospasm requiring intensive treatment in an emergency room or at home, blood dyscrasias or convulsions that do not result in inpatient hospitalization, or the development of drug dependency or drug abuse.

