6.3.2.2 Eliciting and Documenting Adverse Events

All AEs will be assessed from the time the patient signs the ICF until 84 days (12 weeks) after the last dose of study drug or initiation of new anticancer treatment.

Any SAEs that occur more than 84 days after the last dose of study drug do not need to be reported unless the Investigator considers them related to study drug.

At every study visit, patients will be asked a standard nonleading question to elicit any medically related changes in their well-being. They will also be asked if they have been hospitalized, had any accidents, used any new medications, or changed concomitant medication regimens (both prescription and over-the-counter medications).

In addition to patient observations, AEs will be documented from any data collected on the AE page of the eCRF (e.g., clinically significant changes in laboratory values, physical examination,

ECG changes, etc.) or identified from review of other documents that are relevant to patient safety.

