7.6 Statistical Analysis Methodology

7.6.1 Safety Analyses

7.6.1.1 Analyses of Adverse Events

An AE will be considered to be a TEAE if it begins or worsens on or after first dose date and before last dose date + 84 days. Planned summaries of TEAEs are detailed in the statistical analysis plan and will include:

- All TEAEs.
- All serious TEAEs.
- All treatment-related TEAEs.
- All treatment-related serious TEAEs.
- All TEAEs resulting in study drug discontinuation.
- All DLTs.
- Other AE analyses of interest will be specified in the SAP.

The incidence of deaths and the primary cause of death will be summarized.

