#### **4.8.2.2 Deaths**

The following deaths summaries will be generated on the safety analysis set.

- Number (%) of patients who died during the study and reasons for death
- Number (%) of patients who died within 30 days after last dose of study drug except deaths occurred after taking any subsequent anticancer therapy/procedure and reasons for death

All deaths will be listed.

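### The SAP closes the TEAE window at new anticancer therapy, the protocol does not, and the change is undeclared; related events up to Day 84 then leave the by-dose tables, and the rule for collecting them is ambiguous

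*SAP*

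**What the plan says.** Assessment of safety parameters in both parts is a primary endpoint (Protocol 7.2.1). Protocol 6.3.2.1 gives a TEAE definition that has no end date: "any event not present before exposure to study drug or any event already present that worsens in either intensity or frequency after exposure". For analysis, Protocol 7.6.1.1 counts an event as a TEAE "if it begins or worsens on or after first dose date and before last dose date + 84 days". New therapy plays no part in either definition.

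SAP 4.8.2.1 instead keeps the window open "until 84 days (12 weeks) after the last dose date, or start of a new anticancer therapy/procedure, whichever comes earlier". Later events "will not be included in TEAE displays, but will be listed as non-TEAEs". No exception is made for events the investigator rates as related. SAP 4.8.2.2 plans one table of all deaths during the study and a second of deaths within 30 days of last dose, the latter "except deaths occurred after taking any subsequent anticancer therapy/procedure". SAP 3.3 declares one modification, to the efficacy analysis set.

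On collection, Protocol 6.3.2.2 has events assessed from consent "until 84 days (12 weeks) after the last dose of study drug or initiation of new anticancer treatment". Protocol 4.1.10 and footnote 24 of the schedule of procedures use the same unranked *or*. Protocol 6.3.2.2 then adds: "Any SAEs that occur more than 84 days after the last dose of study drug do not need to be reported unless the" investigator attributes them to the drug.

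**The concern.** Patients in this trial have relapsed or refractory disease, and some can be expected to start another treatment within 12 weeks of their last dose. Delayed drug toxicity that appears after that start is counted under the protocol's definition and not under the SAP's. The affected tables include related TEAEs, serious TEAEs, Grade 3 or higher TEAEs and fatal TEAEs, all planned by dose level. Laboratory, ECG and vital-sign summaries also stop at new therapy (SAP 4.8.3 to 4.8.5). For this period, then, no by-dose summary of any of these domains remains. A reader of the study report who relied on the protocol's definition would misread the TEAE rates, and SAP 3.3 would not alert them.

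The collection wording is a second issue. If sites differ in which date they take as the end of collection, the data behind any table or listing after new therapy will be uneven. Protocol 6.3.2.5 treats every serious event at least possibly related to the drug as unexpected and expedited, so uneven collection would matter for reporting as well.

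**Working it through.** The plan gives no figure to reproduce. The check compares the texts, traces one event through them and does a small subtraction.

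**Step 1. The windows side by side**

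| Place | Purpose | End of window |
|---|---|---|
| Protocol 6.3.2.1 | TEAE definition | none stated |
| Protocol 7.6.1.1 | TEAE analysis | before last dose + 84 days |
| SAP 4.8.2.1 | TEAE analysis | earlier of last dose + 84 days and new therapy |
| SAP 6.1.1 | cap on imputed AE onset | last dose + 84 days; new therapy ignored |
| Protocol 6.3.2.2, 4.1.10, footnote 24 | collection | 84 days after last dose *or* new treatment, priority not stated |
| Protocol 6.3.2.2, footnote 24 | related-SAE exception | covers only events more than 84 days after last dose |

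There is also a one-day difference: the protocol's wording ends the window at Day 83, whereas the SAP includes Day 84.

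**Step 2. One event traced.** Count days from last dose. Suppose new therapy starts on Day 30 and a related serious event begins on Day 50.

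- Protocol 7.6.1.1: 50 < 84, so it is a TEAE.
- SAP 4.8.2.1: the window ends at min(84, 30) = 30. Since 50 > 30, the event is a non-TEAE and appears in listings only.
- Collection, if the earlier date governs: it ended on Day 30, so the event is outside.
- Collection, if the later date governs: it ends on Day 84, so the event is inside.
- Collection, if 12 weeks run from new therapy (a possible reading of Protocol 4.1.10 and footnote 24): it ends on Day 30 + 84 = 114, so the event is inside.
- Related-SAE exception: 50 is not more than 84, so the exception does not speak to it.

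**Step 3. Size of the cut.** Let t be the day new therapy starts, counted from last dose. Days lost from the post-dose window = 84 − t. The documents give no value of t, so these are assumptions:

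| t | Days lost | Share of 84 |
|---|---|---|
| 14 | 84 − 14 = 70 | 83% |
| 21 | 84 − 21 = 63 | 75% |
| 30 | 84 − 30 = 54 | 64% |
| 42 | 84 − 42 = 42 | 50% |
| 60 | 84 − 60 = 24 | 29% |
| 84 or later, or never | 0 | 0% |

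This is the tail after last dose only; the on-treatment part of the window is untouched.

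**Step 4. Imputed dates.** SAP 4.8.2.1 promises to classify events with incomplete onset dates as TEAEs unless there is definite contrary information. The onset cap in SAP 6.1.1 nevertheless refers only to last dose + 84 days. The new-therapy date can itself be imputed. If the last dose is on the 20th and therapy is known only to have begun that month, the rule gives the 15th, which precedes the last dose and so becomes last dose + 1, the 21st. The TEAE window then closes one day after dosing on an imputed date.

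**The case against.** Three arguments can be made for the plan as it stands.

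First, the events are not lost. SAP 4.8.2.1 lists non-TEAEs, the listings that follow the TEAE summaries cover all SAEs, and the first table in SAP 4.8.2.2 counts every death during the study regardless of new therapy. This stands, and it rules out the reading that related events disappear from the safety output. Listings do not, however, give rates by dose.

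Second, the cut is not purely the SAP's invention. The protocol's collection text already names new treatment, the SAP applies the same stop across its safety domains, and attribution after another drug has started is difficult. This also stands as a reason why truncation may be defensible. It does not explain why Protocol 7.6.1.1 says otherwise or why SAP 3.3 is silent; it shows that the protocol's own sections need aligning too. Making TEAE status depend on investigator relatedness would put two windows inside one table of an open-label trial, and I do not propose that.

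Third, the reporting rule. A reader might infer that related serious events between new therapy and Day 84 fall outside reporting altogether. The documents do not support that. It follows only if the earlier date governs collection, which the protocol nowhere says. Relief from reporting is given only after Day 84, which implies that earlier serious events remain reportable. Protocol 6.3.2.3 requires every event observed during the study to be recorded and every serious one to be reported, and participation runs through follow-up (Protocol 4.2). The SAP also expects post-therapy events to be in the data, since it plans to list them.

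A reader might further infer a fixed difference in safety follow-up between 3-week and 6-week schedules. That too goes beyond the documents, because time to new therapy is not given. Nor do the schedules separate cleanly: patients moving to 6-weekly dosing after two 3-weekly doses are scanned about 6 weeks after Cycle 1 Day 1, that is 42 − 21 = 21 days after their second dose.

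**Conclusion.** The point holds in two parts of different strength. The conflict between Protocol 7.6.1.1 and SAP 4.8.2.1 is plain from the text. It is undeclared, and it moves related events with onset between new therapy and Day 84 out of every by-dose TEAE table serving a primary safety endpoint. The 30-day death row carries the same cut, and the imputation cap in SAP 6.1.1 does not match the SAP's own window. The collection and related-SAE wording is a genuine ambiguity, not an established exclusion.

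The size cannot be fixed from the documents. Under assumed start days from 14 to 60, between 83% and 29% of the 84-day tail is lost for a patient who starts new therapy, and nothing is lost for one who does not start within 84 days. No event count or change in rate can be derived. The DLT assessment behind the MTD is confined to Cycle 1 and does not use this window, and no hypothesis test is planned. The defect therefore affects the description of delayed toxicity and should be corrected for that reason.

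**What to change.** 1. Use one TEAE window in Protocol 7.6.1.1, SAP 4.8.2.1 and the onset imputation in SAP 6.1.1, including whether Day 84 counts. Otherwise, declare the truncation and its reason in SAP 3.3 and make the imputation rule match.
2. If truncation is kept, add a by-dose summary row of related (or missing-relationship) and serious adverse events with onset through last dose + 84 days, regardless of new therapy. The main TEAE tables can stay as planned.
3. In SAP 4.8.2.2, show deaths within 30 days both with and without those after new therapy.
4. In Protocol 6.3.2.2, 4.1.10 and footnote 24, state which date ends adverse event collection. Then word the related-SAE exception to apply from that end of collection, so that no interval is left uncovered. Changing the exception alone is not enough, because the end of collection is what is undefined.

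The cost is SAP and protocol wording and a few table rows. Some events after new therapy will be hard to attribute, and related-event rates may rise slightly; keeping them in a separate row lets the reader see how much.
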